# **Ending transmission of HIV, HCV, and STDs and overdose in rural communities of people who inject drugs (ETHIC) Including the ECHO addendum**

**NCT#: NCT04427202**

**September 20, 2024**

## **Statistical Analysis Plan**

We will explore the effects on PWUD using longitudinal cohort data from ETHIC participants, where outcomes were guided by the CDC RE-AIM framework. Outcomes of the harm reduction expansion intervention included:

**1.) Reach Analysis:** Reach measures intervention engagement. This was defined as the total number of participants newly engaged in harm reduction services (HRS) by accepting a referral to the HRSO organization with no previous history of receiving services from the organization and at least one week after their baseline survey.

a. Descriptive Analysis: Descriptive analyses will be conducted to examine variable distributions and identify outliers, and data will be summarized using frequencies and measures of central tendency. The absolute number and proportion (%) of participants accepting referral to the harm reduction intervention will be calculated at the end of 2 years. Descriptive and graphical approaches will be used to examine harm reduction engagement over the study period.

**2.) Effectiveness Analysis:** Effectiveness measures the impact of the intervention on outcomes of interest, including evaluation of ECHO/Harm reduction Integration, and will be analyzed as follows;

- a. Descriptive Analysis: Effectiveness will be reported based on the category of outcomes:
  - i. Program Data: Cross sectional analysis of client volume, including primary and secondary exchangers, naloxone trainings and kits dispensed, fentanyl strips dispensed, condoms dispensed, HIV/HCV/STI screenings performed, and clients referred to medical care and substance use treatment will be performed.
  - ii. Injection Behavior: Cross sectional analysis will be performed by calculating the injection behavior outcomes (e.g. syringe/equipment access, sharing practices), i.e. “Effectiveness: Syringes and Equipment outcomes”) in individuals engaged and not engaged in the harm reduction intervention.
  - iii. Overdose: Cross sectional analysis will be performed by calculating the overdose-related behavior outcomes including access to and possession of naloxone (i.e. “Effectiveness: Naloxone outcomes) in individuals engaged and not engaged in the harm reduction intervention.

- iv. Substance use disorder (SUD) treatment: Cross sectional analysis will be performed by calculating referrals to SUD treatment (i.e. “Effectiveness: SUD treatment outcome) in individuals engaged and not engaged in the harm reduction intervention.
- v. HIV care and prevention: Cross sectional analysis will be performed by calculating access to HIV care among those who received a reactive HIV test during the study period, and PrEP knowledge (i.e. “Effectiveness: HIV care access and PrEP outcomes) in individuals engaged and not engaged in the harm reduction intervention
- vi. HCV care: Cross sectional analysis will be performed by calculating access to HCV care among those who received a reactive HCV test during the study period (i.e. “Effectiveness: HCV care access outcome) in individuals engaged and not engaged in the harm reduction intervention
- vii. Sexual Behavior: Cross sectional analysis will be performed by calculating the sexual-related behavior outcomes including engaging in condomless sex (i.e. “Effectiveness: Sexual behavior outcomes) in individuals engaged and not engaged in the harm reduction intervention.

In addition to descriptive analyses of these secondary outcomes, we will explore longitudinal differences from baseline and 6 months among those who were newly engaged in HRS.

- 3.) Adoption Analysis: Adoption of the intervention by the harm reduction agency will be defined by the number of additional participants and additional zip codes served by the end of the study period.
- 4.) Implementation Analysis: The fidelity, acceptability, appropriateness, feasibility, cost, and maintenance / sustainability of the intervention will be analyzed as follows:
  - a. Fidelity
    - i. Field staff observation using the WHO 15 essential element needle exchange program checklist at baseline and every 6 months thereafter will be analyzed based on adherence to each element of service provision, with fidelity as a measure of 100% compliance at 6 months, and maintenance of fidelity defined by 100% compliance at all subsequent observations.
    - ii. Qualitative analysis: The qualitative instruments will be based on CFIR constructs as described above in the Narrative Study Design section. At the conclusion of each interview, the interviewer will develop a broad free-text memo detailing any prevailing observations or interpretations from the interview. These interview memos will then be reviewed and discussed with another member of the research team. Interviews will be transcribed and will be analyzed using a deductive thematic approach using NVivo. This process will be prefaced by the development of a set of *a priori* codes, generated using the CFIR framework as the basis for

the coding scheme. Each transcript will be coded by one coder; for additional fidelity, a second coder will code a subset of transcripts. Discrepancies will be resolved through discussion.

- b. Acceptability, Appropriateness, and Feasibility:
  - i. Qualitative analysis: The qualitative instruments will query on elements of the Acceptability of Intervention (AIM), Intervention Appropriateness (IAM), and Feasibility of Intervention (FIM) measures. Qualitative exploration (as opposed to surveys) was chosen given the small sample size and richness of data and contextualization offered via the semi-structured interview format. Interviews will be analyzed as per section 4.a.ii. above, with the development of a set of *a priori* codes, generated using the Weiner's measures as the basis for the coding scheme. Each transcript will be coded by one coder; for additional fidelity, a second coder will code a subset of transcripts. Discrepancies will be resolved through discussion
- d. Maintenance and Cost Analysis:
  - i. Qualitative analysis: To explore Maintenance of the intervention, the qualitative instruments will also query on elements of The Program Sustainability Assessment Tool (PSAT), again modified to be elicited as items in the interview guide given the small sample size of stakeholders and the richness of qualitative data. Interviews will be analyzed as per section 4.a.ii. above, with the development of a set of *a priori* codes, generated using the PSAT as the basis for the coding scheme. Each transcript will be coded by one coder; for additional fidelity, a second coder will code a subset of transcripts. Discrepancies will be resolved through discussion.
  - ii. Cost analysis: The cost analysis will be performed using Cidav's pragmatic approach, which combines granular, procedurally based time-driven activity-based costing of implementation activities (intervention and implementation strategies) as characterized above. Cost per HRSO participant served per year was calculated, as well as the annual budget impact of service expansion based on adoption over the course of the study. Costs were discounted at 3% annually. Costs relate to research, including data collection and research overhead will be excluded.

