- k) Referral to harm reduction services (HRS) . For those participants not engaged in harm reduction (ie not directly referred by CAP), a referral will be made to these services. Evidence-based services offered through CAP will include five core services: syringe services; naloxone training and dispensing; referral to substance use treatment; infectious disease screening and referral to treatment and vaccination; and education/counseling around sexual/injection drug risk behavior, including condom and fentanyl test strip distribution. Initial engagement/enrollment in the harm reduction intervention will be defined as acceptance of any service at the time of referral. Participants who refuse initial referral will be offered referrals at each of the 6 month follow up encounters.
- l) Evaluation of Harm Reduction Service provision using qualitative data collection. We will interview the harm reduction staff at Community Action Place, Inc. (CAP) (3). These interviews will be performed as part of the implementation analysis to identify barriers and facilitators to provision of harm reduction services, including factors impacting participant outreach, engagement, retention, linkage, and referral to treatment services. The interview guide will be developed using the Consolidated Framework for Implementation Research (CFIR) conceptual framework developed to guide systematic assessment of multilevel implementation contexts to identify potential determinants of intervention implementation. Interviews will last approximately 60 minutes. Following the interviews, staff members will be asked to complete a brief demographic survey. The information captured through this survey will be used to help us contextualize the background and general traits of these participants. Interviews will be audiotaped, transcribed verbatim, and then edited to remove personal identifiers from the finished copy.
- m) Evaluation of Harm Reduction Service engagement through analysis of Community Action Place, Inc. client services data. Data to be used for the analysis includes number of client visits, syringes / equipment / condoms distributed, naloxone training and kits distributed, referrals and linkages to treatment.

Figure 1. Flowchart for Study Enrollment and Procedures for PWUD

[figure not shown]
[figure not shown]

Figure 2. Flowchart for Study participants

4) Eligible participants

a) Type and number of subjects

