 - 2.) Effectiveness Analysis: Effectiveness measures the impact of harm reduction referral on outcomes of interest as follows;
 - i. Injection Behavior: Cross sectional analysis will be performed by calculating the injection behavior in individuals engaged and not engaged in the harm reduction intervention.
 - ii. Overdose: Cross sectional analysis will be performed by calculating the overdose-related behavior outcomes including access to and possession of

naloxone in individuals engaged and not engaged in the harm reduction intervention.

- iii. Sexual Behavior: Cross sectional analysis will be performed by calculating the sexual-related behavior outcomes including access to and possession of naloxone in individuals engaged and not engaged in the harm reduction intervention.
- iv. MAT / other substance use disorder treatment: Cross sectional analysis will be performed by calculating access to SUD, including MAT in individuals engaged and not engaged in the harm reduction intervention.
- v. HIV care and prevention: Cross sectional analysis will be performed by calculating access to HIV care and PrEP in individuals engaged and not engaged in the harm reduction intervention.
- vi. HCV care: Cross sectional analysis will be performed by calculating access to HCV care in individuals engaged and not engaged in the harm reduction intervention.
- vii. Stigma: Cross sectional analysis will be performed by calculating access to SUD, including MAT in individuals engaged and not engaged in the harm reduction intervention.
- viii. Program Data: Cross sectional analysis of client volume, including primary and secondary exchangers, naloxone trainings and kits dispensed, fentanyl strips dispensed, condoms dispensed, HIV/HCV/STI screenings performed, and clients referred to medical care and substance use treatment will be performed.

3.) Adoption Analysis: Adoption of the harm reduction intervention will be defined by i) Utilization and ii) Self -reported access outcomes, stratified by service type:

- i. Utilization of any services ≥ 2 in the past six months/participants accepting referral (Adoption: absolute (%) outcome),
- ii. Self-reported access to services (Adoption: syringe, naloxone, MAT, and condom outcomes)

4.) Implementation Analysis: The fidelity, acceptability, appropriateness, feasibility, and cost of the intervention, and the examination of the RDS-based mechanism as referral into services will be analyzed as follows:

- a. Fidelity

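### SAP 2.a.iv replaces access to SUD treatment with SUD referrals, one of the agency's own services, so the engaged/not-engaged contrast partly measures service delivery

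*SAP*

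**What the plan says.** **The outcome in the SAP.** Section 2.a.iv (Effectiveness, SUD treatment) states: "Cross sectional analysis will be performed by calculating referrals to SUD treatment", compared between people engaged and not engaged in the harm reduction intervention. The result is labelled as the SUD treatment outcome.

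**The outcome in the protocol.** Section 8, item q) 2.) iv, headed as MAT and other SUD treatment, plans "calculating access to SUD, including MAT in individuals engaged and not engaged in the harm reduction intervention".

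**The intervention.** Protocol section 3 k) lists the agency's "five core services: syringe services; naloxone training and dispensing; referral to substance use treatment", followed by infectious disease screening and referral, and education and counselling.

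**The exposure.** Two definitions exist.
- Protocol section 3 k): "Initial engagement/enrollment in the harm reduction intervention will be defined as acceptance of any service at the time of referral".
- SAP section 1 (Reach): participants "newly engaged in harm reduction services (HRS) by accepting a referral to the HRSO organization with no previous history of receiving services", at least one week after the baseline survey.

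The SAP does not say which of these forms the Effectiveness groups.

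**Referrals elsewhere in the SAP.** Section 2.a.i (Program Data) is a cross-sectional count of agency activity. Its list ends with "clients referred to medical care and substance use treatment will be performed". It has no engaged/not-engaged contrast.

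**The concern.** The outcome chosen to show an effect on SUD treatment is something the agency itself delivers to people who engage. A higher referral rate among the engaged is then expected from the way the programme works, whether or not anyone additional starts treatment. Adjusting for differences between the groups would not remove this, because it comes from the overlap of outcome and exposure and not from confounding.

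Two things are at stake. The first is interpretation: the SAP presents Effectiveness as measuring the intervention's impact, so the contrast will be read that way. The second is what is lost. The background to the ECHO addendum describes poor access to SUD treatment as a main problem in the region: 13% of respondents had any SUD support in the past 30 days, and 70% were unsure about access to buprenorphine or expected it to be difficult. As written, the SAP would not show whether engagement changes that.

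**Working it through.** The documents give no sample size, power or expected rate for this outcome, so there is no planned figure to reproduce. The check compares definitions first and then illustrates the size.

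**Step 1. Overlap of outcome and exposure.**
- Protocol definition: engagement is acceptance of any core service, and SUD referral is a core service. Accepting an agency SUD referral at the time of referral is therefore sufficient to be classed as engaged. The overlap is definitional, but partial, because people may engage through another service.
- SAP Reach definition: engagement is accepting a referral to the organization, which is a different event from being referred to SUD treatment. The overlap is then structural: those who go to the agency are the ones to whom it offers SUD referral.

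**Step 2. Source in each group.** SAP 2.a.iv names no data source. Referrals are counted explicitly in two places, protocol section 3 m) (agency client services data) and SAP 2.a.i (Program Data), and both describe clients. Survey and interview data are also listed sources for the evaluation (protocol section 8 q). The source for the not-engaged group is thus unspecified.

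**Step 3. What other SUD treatment outcome remains.**
- HIV care and HCV care stay as access outcomes in SAP 2.a.v and 2.a.vi. Only SUD moves back to referral.
- The protocol's Adoption analysis included self-reported MAT access. SAP section 3 defines Adoption by additional participants and zip codes served.
- No measure of SUD treatment access or receipt is left in the SAP.

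**Step 4. Illustrative size with no true effect.** Assumptions, none of them document figures for referral:
- *b*: background probability of an SUD referral from any other source, equal in both groups. The value 13% is borrowed from the addendum's figure for SUD support received, which is receipt and not referral.
- *s*: share of engaged people who take an agency SUD referral, independent of background referral.

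Engaged rate = s + (1 − s)b. Not-engaged rate = b. Built-in difference = s(1 − b).

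| s | Engaged rate at b = 13% | Not engaged | Built-in difference |
|---|---|---|---|
| 5% | 17.4% | 13% | 0.05 × 0.87 = 4.4 points |
| 10% | 21.7% | 13% | 0.10 × 0.87 = 8.7 points |
| 20% | 30.4% | 13% | 0.20 × 0.87 = 17.4 points |
| 30% | 39.1% | 13% | 0.30 × 0.87 = 26.1 points |

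Over b = 0 to 30% and s = 5 to 30%, the difference runs from 0.05 × 0.70 = 3.5 points to 0.30 × 1.00 = 30 points. Under this model it is above zero whenever s is above zero and b is below 100%.

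**The case against.** The strongest reply is that the SAP has its own engagement wording. Under it, accepting a referral to the agency is not the same event as a referral to SUD treatment. That stands, and it means the outcome overlaps the exposure but is not identical to it.

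A reader might go further and infer that not-engaged participants have no SUD referrals by definition, or that no comparable measure exists for them. The documents do not support either reading:
- Nothing in SAP 2.a.iv restricts referrals to those made by the agency, so another provider's referral could count.
- Recruitment draws partly on existing agency clients. The SAP's newly engaged group excludes people with prior services, so existing clients holding agency referrals might fall among the not engaged.
- Survey data are a listed source, all survey participants are asked about health care utilization, and the survey instrument is not in the text available. A referral item cannot be ruled out.

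A zero rate among the not engaged would follow only if agency records were the sole source and the not-engaged group contained no agency clients. Nor do the documents say that the referrals in 2.a.iv are the same records counted in 2.a.i.

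Three further replies carry some weight. Syringe and naloxone provision are also core services with matching effectiveness outcomes, so the overlap is not unique to SUD; those outcomes do, however, include access or possession, whereas a referral is an act of the provider. The uptake values are assumed, and at 5–10% uptake the built-in difference is only about 4 to 9 points at b = 13%. Finally, the SAP calls the analysis descriptive and the outcomes secondary, and attaches no test or decision rule to this item. This limits the severity but does not remove the problem of interpretation.

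**Conclusion.** The concern holds. The SAP replaces a treatment access outcome with a process output of the intervention and compares that output between groups formed by engagement with the same intervention. The overlap is definitional under the protocol's rule and structural under the SAP's Reach rule. In both cases part of the contrast reflects service delivery, and it tends to favour the intervention with no effect on treatment entry. The SAP leaves the referral source in the not-engaged group unstated and retains no SUD treatment access or receipt outcome.

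The illustrative built-in difference is about 4 to 26 points. It rests on an assumed uptake of 5–30%, an assumed background rate of 13% in both groups, and independence of the two. The direction is firmer than the size.

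Severity is moderate: this is a descriptive secondary outcome, and the risk lies in how the contrast will be read, not in an invalid formal test.

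**What to change.** 1. In SAP 2.a.iv, use self-reported access to, or receipt of, SUD treatment including MAT from the six-monthly participant survey, with the same item and the same time window in both groups.
2. Keep SUD referral counts under SAP 2.a.i as a process measure, without an engaged/not-engaged contrast.
3. State which engagement definition forms the Effectiveness groups, who counts as not engaged, and where existing agency clients fall. This also helps readers interpret the syringe and naloxone outcomes.

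The cost should be SAP wording. The protocol already planned the access outcome, and the addendum's figures show that the survey has collected data on SUD support and on perceived access to buprenorphine. The exact item should be confirmed against the instrument. The downside is a probably smaller and less favourable contrast. The change does not address self-selection into engagement, which remains a separate limitation.

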Proposals for multi-site analyses using harmonized, multi-site datasets, including ETHIC and other sites' data, will be overseen by the ROI Publications Working Group. The ROI Publications Working Group shall maintain representation from each of the eight ROI sites, including Illinois and the ROI DCC. Any researcher interested in developing manuscripts or other scientific materials using harmonized, multi-site datasets, will be required to submit a proposal narrative to the ROI Publications Working Group. Proposal narratives should be submitted for the approval of all journal articles, research papers, conference abstracts, new grants, or other format of dissemination derived from any The ROI DCC shall not to share the ETHIC dataset with anyone outside the ROI consortium, but may share harmonized, multi-site, project-specific datasets containing ETHIC data with researchers at other ROI consortium sites after approval of a proposal by the ROI Publications Working Group, including an affirmative vote from the ETHIC team representative.

Limited identifiers (zip code and county of residence) will be shared with Ohio State University from 173 subjects that were enrolled between 8/2017 - 7/2019 for analysis. These identifiers will be used to supplement data currently available through DCC.

Before any data transfer, the University of Chicago will encrypt the data both at rest and in transit via a Shared File Transfer protocol (SFTP) to provide a high level of security of sending and receiving file transfers. The encrypted data products will be securely uploaded to a SFTP server using a cyberinfrastructure service such as Globus (<https://www.globus.org/>) via the Biological Science Division Information Services (BSDIS). Using a STFP will ensure high security

features that meet authentication and authorization standards for sensitive data containing protected health information. Additionally, data management and transferring services for personally identifiable data will be with a High Assurance or HIPAA BAA subscription. If an institution is responsible to provide data (incoming), they will be responsible for encryption.

10) Duration of protocol

Data collection, data analysis and dissemination to partners is expected to take 36 months.

11) Potential risks to study participants

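### The SAP discounts costs at 3% a year, yet its only two named cost results are annual figures; applied as written, the rule modestly understates later years

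*SAP*

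**What the plan says.** SAP section 4.d.ii (Maintenance and Cost Analysis, Cost analysis) describes time-driven activity-based costing and then names two results. The first is a unit cost: "Cost per HRSO participant served per year was calculated". The second is "the annual budget impact of service expansion based on adoption over the course of the study". The next sentence is "Costs were discounted at 3% annually". The section then excludes research costs. It does not limit the discounting to any particular output, and it states no base year, price year, inflation adjustment or costing horizon.

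No other section fills the gap. SAP section 3 defines adoption by "the number of additional participants and additional zip codes served by the end of the study period" and mentions no discounting of those counts. The protocol, in section 8.q.4 (Implementation Analysis), lists cost among the outcomes, in the words "The fidelity, acceptability, appropriateness, feasibility, and cost of the intervention", but gives no costing method.

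**The concern.** A year's budget impact is the money needed in that year. Discounting restates that money at its value in an earlier year, which is a different quantity. It is the right tool when costs from several years are added into one present value, but the SAP names no such total. As the text stands, the 3% rate has nothing to act on except the two annual results.

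For the unit cost there is a second effect. The numerator is discounted while participants are counted as they are, so each later year's ratio is multiplied by a further 1/1.03 whatever the service does. Nor is discounting an inflation adjustment: putting several years on a common footing needs a stated price year, and none is given.

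At stake is whether the reported annual figures can be read as what the service cost in each year, and whether a trend in unit cost across years reflects the service or the discount rate.

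**Working it through.** The documents give no cost result to reproduce. The check is therefore of what the stated rule does to an annual figure.

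**Inputs**
- Discount rate: 3% a year (SAP section 4.d.ii).
- Participant counts: no discounting stated (SAP section 3).
- Horizon: not stated for the costing. Two periods appear elsewhere. The SAP Reach analysis (section 1.a) has the proportion "accepting referral to the harm reduction intervention will be calculated at the end of 2 years". Protocol section 10 says "Data collection, data analysis and dissemination to partners is expected to take 36 months"; this includes analysis and dissemination, so the costed period may be shorter.
- Base year: not stated. Year 1 as base is an assumption; two other conventions are shown for range.
- True yearly growth in unit cost, g: not given in the documents, so a range is assumed.

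**Step 1. Understatement in each year.** With year 1 as base the factor for year t is 1/1.03^(t−1), and the understatement is 1 minus the factor.
- Year 1: factor 1.0000, understatement 0%.
- Year 2: 1/1.03 = 0.9709, understatement 2.91%.
- Year 3: 1/1.03² = 0.9426, understatement 5.74%.

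A constant $100 per participant, used only as an illustration, would be shown as $100.00, $97.09 and $94.26.

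**Step 2. Cumulative understatement with flat spending.**
- Two years: 1 − (1 + 0.9709)/2 = 1.46%.
- Three years: 1 − (1 + 0.9709 + 0.9426)/3 = 2.88%.

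**Step 3. Sensitivity to the base-year convention.** The mid-year factor is 1/1.03^(t−0.5) and the end-year factor is 1/1.03^t.

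| Convention | Year 1 | Year 2 | Year 3 | Cumulative, 2 years | Cumulative, 3 years |
|---|---|---|---|---|---|
| Year 1 as base | 0% | 2.91% | 5.74% | 1.46% | 2.88% |
| Mid-year | 1.47% | 4.34% | 7.12% | 2.90% | 4.31% |
| End-year | 2.91% | 5.74% | 8.49% | 4.33% | 5.71% |

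**Step 4. Effect on the trend in unit cost.** With undiscounted counts, the apparent yearly change is (1 + g)/1.03 − 1, whichever convention is used.
- g = 0%: −2.91%
- g = 2%: −0.97%
- g = 3%: 0.00%
- g = 5%: +1.94%

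The drift is always downward by a factor of 1/1.03 a year. Whether the reported unit cost actually falls depends on g.

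**The case against.** The strongest reply is that the SAP does not say where the rate was applied. It could have been used only for a total that the text leaves unnamed, or to annualise start-up costs, and then the annual figures might be unaffected. Nor does the SAP say that results appear as a year-by-year series. The unit cost could be one pooled figure, total cost over participant-years, and the budget impact one annualised figure. A pooled figure shows no year-to-year decline, although its level would still be understated if discounted costs went into it.

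This lowers confidence but does not remove the point. The sentence is unqualified, it directly follows the two annual results, and nothing else in either document restricts it. A reader who follows the SAP literally gets annual figures that are not what was spent.

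Three stronger readings are tempting, and the documents do not support them.
- A reader might infer that unit cost must appear to fall. It does so only if true unit cost grows by less than 3% a year; above that, discounting hides part of a rise. Changes in volume as the service expands could also move unit cost, and no cost data are given.
- A reader might extend the calculation to a fifth year or beyond for a larger effect. The only horizons in the documents are 2 years and 36 months.
- A reader might infer that a health department or other funder would be given too low a budget. The documents describe no such use of the figure, and they attach no threshold or decision rule to it.

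**Conclusion.** The point holds as a minor one, with medium confidence. The stated rule does not fit the stated outputs: both named cost results are annual, and an unqualified 3% discount turns each into an earlier-year value while adding a downward drift of about 2.9% a year to the true unit-cost trend.

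Taking year 1 as the base, the understatement is 2.9% in year 2 and 5.7% in year 3 if a third year is costed. Cumulatively it is about 1.5% over two years and 2.9% over three with flat spending. Under end-year discounting, year 1 is also understated, by 2.9%, and year 3 by 8.5%.

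These sizes rest on three assumptions that the SAP does not settle: that the rate was applied to the annual results, which year is the base, and how many years were costed. The cost analysis is a descriptive implementation outcome with no hypothesis test, so no inferential result depends on it.

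**What to change.** In SAP section 4.d.ii, replace the discounting sentence with text that does three things:
1. Reports the yearly cost per participant and the annual budget impact undiscounted, converted to one stated price year, with the method of price adjustment named.
2. Restricts the 3% rate to a separately labelled multi-year present-value total, if one is given, with its base year and horizon.
3. States which years are costed, and whether the annual results are shown year by year or pooled.

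The cost is a short SAP edit and, if the annual results were in fact discounted, a recalculation from cost data already held. No new data are needed. Removing the discount would make later-year costs slightly higher, by the percentages above. If the rate was never applied to the annual results, only the wording changes.
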